7.2 Products and reference products

The following materials are used in the clinical study:

conditioning agents:

Total Etch - Gel for enamel etching and dentine conditioning for direct filling therapy with composites

Adhesive system: Adhese Universal - Bonding agent between dentin or enamel and composite

Composite restoratives:

- Test product: The flowable composite - light-curing flowable bulk composite filling material as first increment (maximum 4 mm).
- Test product: F-Composite 2- light-curing modellable composite filling material as obligatory covering layer of at least 1 mm

Polymerization lamp:

- Bluephase PowerCure with flash mode for polymerization of the adhesive and the composites in 3 s each.

The conditioning agent, the adhesive and the flowable composite have already been introduced to the market and have proven to be clinically effective.

7.3 Participants (In-/Exclusion criteria)

a) inclusion criteria for the selection of participants

- Age: 18-65 years
- 40-60% women, 40-60% men
- Indication for a direct filling of class I or II in permanent premolars or permanent molars
 - Replacement of insufficient fillings (e.g. due to marginal caries, fracture of the filling, poor surface quality, poor aesthetics, unwanted filling material, leaky margin, marginal gap, etc.)
 - extensive primary caries
- Vital tooth (cold test)
- Single-, double- or triple-surface fillings in the posterior region, where a maximum of 25% should be single-surface fillings (class I) with antagonists.
- The occlusally assessed area of the filling must be at least 1/3 of the total area of the tooth. This criterion is estimated.
- Participant wishes to receive care within the scope of the study (written declaration of consent after detailed explanation and study of the patient information).
- Maximum 2 restorations per patient.
- Preoperative complaints on the tooth to be restored (maximum 3 on visual analogue scale (0= no complaints, 10= maximum possible pain) due to temperature stimulus or sensitivity to bite
- Sufficient German language skills

b) exclusion criteria for the selection of the participant.

- Not completed hygiene phase or poor oral hygiene
- Sufficient drainage of the surgical field not possible
- Patients with a proven allergy to one of the ingredients of the materials used
- Patient is allergic to ingredients of the local anaesthetic Ultracain DS (active ingredient: articaine; vasoconstrictor), if anaesthesia is desired
- Patients with severe systemic diseases
- Devital or pulpit teeth
- Periodontally insufficient dentition
- Restorations with cusp abutments
- open lateral bite
- missing antagonist
- Indication for direct capping
- Pregnancy (women of child-bearing age receive a free pregnancy test for self-testing in advance, the negative result of which they document with their declaration of consent)

c) Patients discontinue the study on their own initiative or withdraw for reasons that make further assessment of the filling impossible. These include, for example, extraction of the tooth due to a cause independent of the study, the change in the opposing dentition or treatment by an external dentist.

These patients are considered to be drop-out and are reported separately with the drop-out cause (CRF V). The recall data obtained up to the time of drop-out are used in the analysis.

d) the date of recording.

After a positive ethics vote and registration at "clinicaltrials.gov", the study will start, i.e. this marks the earliest point of admission.

e) Expected total duration of the clinical investigation.

The expected total duration of the clinical investigation is 5 years and 4 months.

f) The expected duration of participation of each participant in the treatment scheme in Table 1 is 5 years (60 months).

g) The required number of participants to be included in the clinical investigation shall not exceed 75.

h) The estimated time needed to obtain this number of participants (i.e. recording time) is estimated at 4 months.

7.4 Treatments

a) Description of all treatments administered to the investigation participants during the clinical investigation Three operators place 25 fillings each.

Preparatory measures and cavity preparation

- A medical and dental anamnesis and detailed findings are taken for each patient and, if necessary, x-rays are taken. A visual analogue scale is used to record the preoperative complaints of the tooth to be restored with regard to temperature stimulus and bite sensitivity. However, no cold or bite sensation is set for this purpose. The vitality is checked with a cold spray. In addition, a therapy plan is drawn up in accordance with the restoration concept.
- A digital photo of the initial state is taken. The vestibular and oral views are printed out. The occurrence and extent of horizontal tears are drawn on it.
- If possible, rubber dams are used for drainage. If a rubber dam is not possible, an appropriate relative draining method is used (OptraGate, cotton rolls, saliva ejector).
- Then the insufficient filling or caries is removed.
- The preparations are done with 80 µm diamonds, a finish of the cavity edges with 25 µm diamonds. The cavity edges in the enamel are chamfered, but not gingivocervically.

Measurement of the cavity and renewed documentation of melt cracks

- A digital photo of the prepared cavity is taken
- The lowest point of the respective proximal boxes and occlusal pull-through is measured with a PA probe (Hu-Friedy PCPUNC 15) and documented on the CRF I. The reference for the proximal box is the proximal-occlusal cavity margin in the marginal ridge area and, for determining the occlusal pull-through depth, the occlusal cavity margin adjacent to the lowest point. The determination should be made with an accuracy of ± 1 mm.
- The average width of the cavity is given in absolute terms (accuracy ± 1 mm). The already mentioned periodontal probe is also used as an aid here.

- Prior to conditioning, the tooth is again examined for horizontal enamel cracks, which are recorded in the printed photographs in terms of their extent and localization and recorded on the CRF I. A cold-light fibre optic (light probe by Lercher) is used as an aid.
- The residual dentin thickness above the pulp is determined with a prepometer at the site with the lowest layer thickness (Wegehaupt et al. (2009)).

The partial matrix system from Garrison (Compositight) or Triodent (V3) is used as the matrix.

Application of the etching gel and adhesive system

- According to GI in Etch&Rinse mode, exposure time of Total Etch in enamel 30 s, dentin 10-15 s. The adhesive must be rubbed in for 20 s.
- The adhesive is cured with the Bluephase PowerCure in flash mode for 3 s.

Application of the composite in the bulk fill technique

- Application of the flowable composite in a horizontal layer of maximum 4 mm, taking into account the minimum layer thickness of the top layer.
- Application of F-Composite 2 in layers of max. 4 mm. To simplify the design of the anatomy, several oblique increments are permitted as cover layer. The minimum layer thickness of the top layer is 1 mm.
- Light polymerization per layer for 3 s with Bluephase PowerCure (flash mode, 3000 mW/cm²)
- Finishing of the filling with composite shape diamonds and final polishing with the one-step polishing system OptraPol (Ivoclar Vivadent)

b) Apart from monitoring, there are no other activities carried out by representatives of the sponsor (IvoclarVivadent AG).

c) A distortion of the results could arise from the following factors:

- Mainly older patients (> 45 years) are included in the study. Older patients are less prone to post-operative hypersensitivity than younger patients due to pulp retraction caused by secondary dentin.
- The replacement of insufficient fillings or the treatment of primary carious lesions results in shallow cavities with a residual dentine thickness of 1.5-3 mm. A greater residual dentin thickness may reduce the risk of pulp irritation caused by the high light intensity of the polymerization light and thus the number of postoperative hypersensitivities. Small to medium-sized cavities also reduce the risk of horizontal enamel cracks.
- Due to the explanatory talk of the participants or the knowledge of the operators, both participants and operators could be sensitized regarding the important clinical parameter "post-operative hypersensitivity" and thus falsify the result.

If material-dependent problems occur that require replacement of the F-Composite 2 fillings, a replacement filling made of established standard materials is placed free of charge. No further medical care is planned after the test.

7.5 Specifications for monitoring

This clinical investigation will be monitored by the sponsor at defined timely intervals. The Monitoring Plan lists the activities within the scope of monitoring.

8. Statistical considerations

- a) Due to the study design, no special statistical methods are necessary.
- b) The sample size is 75 fillings
- c) validity of the clinical investigation: the system is suitable for the market if the acceptance criteria are met.
- d) Expected drop-out rate: Analysis of older comparable studies show that an annual drop-out rate of 2% can be expected. Accordingly, three fillings could no longer be checked after 2 years.
- e) Acceptance criterion for post-operative hypersensitivity after 4 weeks: $\leq 10\%$ (=6 fillings).
Acceptance criterion for loss of vitality after 1 year: maximum 1 restored tooth
Acceptance criterion for filling replacement after 2 years: maximum 3 fillings
- g) If more than 50% of the patients suffer from postoperative hypersensitivity after placing at least 20 fillings, the study would be terminated.
- k) If patients discontinue the study or drop out for other reasons (including extraction of the tooth from a cause not related to the study, change of the opposing dentition or treatment by an external dentist), they are considered a drop-out and are reported separately with the drop-out cause (CRF V).
The recall data obtained up to the time of withdrawal from the study are used in the evaluation.

9. Data management

- a) Data verification is carried out with plausibility checks. The data is encrypted, since the patient names do not appear in the data tables, but the cases can be assigned using case numbers and patient IDs.
- c) The archiving of the data takes place on the company's secure servers. The data is stored as SPSS data sheets in anonymized form. The traceability is given by case numbers.
- d) The retention period of the data after completion of the study is 10 years.

Since all persons involved in the study, especially the operators and the evaluator, are familiar with and apply the company's internal guidelines regarding "Good Documentation Practice" (SOP-00081-EN; Good Documentation Practice), the traceability of changes is ensured by the dating and sizing of corrections.

CRFs, radiographs and clinical images will be collected as source data in this study.

Authorities and the Monitor will be granted access to the original data at any time, should this be necessary.

If a participant withdraws his or her consent, the health-related personal data will be made anonymous after the data evaluation is completed. Despite revocation, the participant will be offered follow-up treatments to the extent required to protect his or her health.

10. Changes to the clinical investigation protocol

Substantial changes to the approved clinical investigation must be approved by the Ethics Committee prior to their implementation. Excepted from this obligation are measures that must be taken immediately to protect the participating persons.

The following are considered to be significant changes:

- Changes that affect the health and safety of the participating persons or their rights and obligations
- changes in the study plan, in particular changes due to new scientific evidence concerning the test design, test method, objective criteria or statistical design;
- the change of the place of execution or the execution of the clinical investigation at an additional place of execution;

the change of sponsor, coordinating investigator or investigator-in-charge at a site.

All other changes are submitted to the Ethics Committee once a year together with the safety report.

Substantial changes to the approved clinical investigation must be approved by the Liechtenstein Office of Public Health before they are implemented. This obligation does not apply to measures that must be taken immediately to protect the participating persons.

In this context, significant changes are considered to be substantial:

- Changes to the medicinal product or its administration or use;
- Changes due to new preclinical and clinical data that may affect product safety;
- Changes concerning the manufacture of the medicinal product which may affect product safety.

Other changes concerning documents submitted to the Office of Public Health must be notified to the Office of Public Health as soon as possible.

11. Deviations from the clinical investigation protocol

The investigator is not permitted to deviate from the CIP, except under emergency conditions to protect the rights, safety and health of the participant. If safety and protective measures must be taken immediately during the conduct of the clinical investigation, the investigator must notify the Ethics Committee within two days of these measures and of the circumstances which made them necessary.

In such a case, the sponsor must also submit a report to the Office of Public Health.

12. Proof of use of the product

The proof of use of the test product shall be documented as described in 6.9 of EN ISO 14155:2011.

13. Declaration of conformity

All groups involved in the investigation, as well as their individual members, undertake at all times during the investigation to

- the Declaration of the World Medical Association of Helsinki,
- local legislation
- the EN ISO 14155:2011
- the clinical investigation plan to be observed.

The investigation may not begin before the approving opinions of the competent ethics committee and the supervisory authority have been received.

Possible additional requirements of the ethics committee or the supervisory authority must be observed.

All patients participating in the clinical examination are insured against damages caused by the examination material.

14. Procedure for obtaining consent

The patients are informed orally and in writing about the course of the experiment, the materials to be tested and any risks and sign a corresponding declaration of consent. Before the patient concerned decides on the consent, he/she is given a period of reflection of at the latest 3 working days. Every patient has the right to refuse further participation in the study at any time.

According to the patient information, the participant will be informed immediately if at any time during the conduct of the study aspects should arise that could influence the willingness of patients to participate in the study.

15. Adverse events, adverse effects of the product and product defects

All incidents that are detrimental to the patient, whether or not they are caused by the object of investigation, are undesirable incidents. If these adverse events are due to the object of investigation, they are adverse effects. Each of these adverse reactions must be documented on the follow-up examination form (CRF IV). The clinical investigator must decide whether or not the adverse reactions could have been caused by the materials under investigation and thus whether or not an adverse effect exists.

A serious adverse event (SAE = Serious Adverse Event), which cannot be ruled out as being attributable to the investigational product or to an intervention carried out in a clinical investigation, is reported to the Cantonal Ethics Committee in Zurich within 7 days. In addition, a report must be made to the Liechtenstein Office of Public Health within 7 days ("Reporting form for clinical investigations with medical devices - Serious Adverse Event").

A serious adverse event in this study is an event that

- (a) resulted in death
- (b) resulted in a serious adverse health effect to the participant, which was either
 - 1) results in a life-threatening disease or injury, or
 - 2) results in a permanent impairment of a body structure or function, or
 - 3) results in hospitalisation or the extension of an existing hospital stay, or
 - 4) involves a medical or surgical procedure to prevent a life-threatening disease or injury or permanent impairment of a body structure or function

Once a year, a safety report (ASR) is submitted to the Ethics Committee and the Office of Public Health, which contains a list of events (SEA) and establishes their causality for intervention and assesses the safety of the participating patients

If undesirable events occur that require treatment outside the practice, follow-up treatment is ensured by means of a detailed referral to the relevant specialist, family doctor or, if applicable, family dentist.

16. Population that can be pressured

During the planned clinical investigation, the investigational product will not be applied to populations that can be put under pressure.

17. Premature termination or suspension of the examination

The study can be terminated by the dentist, the sponsor or the manufacturer of the drugproduct. The following reasons can lead to this:

- technical problems during the manufacturing process
- Adverse events related to the testproduct that threaten the safety and health of the investigation participants (unacceptable risks)
- lack of compliance (willingness to cooperate) of a patient

Any interruption of the study must be reported to the Ethics Committee and the Office of Public Health within 15 days. An interruption or the regular end of the study must be reported to both institutions within 90 days. The final report must be submitted to the Ethics Committee and the Office of Public Health within one year of the end of the study.

No study follow-up beyond the duration of the study is foreseen.

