Clinical Investigation Protocol (incl. statistical considerations)

Clinical examination of the F-Composite 2 Systems in the direct filling therapy

(NCT03221660)

INDEX

1. OBJECTIVES AND HYPOTHESES OF THE CLINICAL INVESTIGATION	3
2. GENERAL OVERVIEW OF THE CLINICAL INVESTIGATION	4
3. JUSTIFICATION FOR THE STRUCTURE OF THE CLINICAL INVESTIGATION.....	4
4. INVESTIGATORS	5
5. MATERIALS	5
6. RISKS AND BENEFITS OF THE INVESTIGATIONAL PRODUCT AND THE CLINICAL INVESTIGATION	6
7. STRUCTURE OF THE CLINICAL INVESTIGATION.....	7
7.1 GENERAL INFORMATION	7
7.2 PRODUCTS AND REFERENCE PRODUCTS	8
7.3 PARTICIPANTS (IN-/EXCLUSION CRITERIA).....	9
7.4 TREATMENTS	10
7.5 SPECIFICATIONS FOR MONITORING	11
8. STATISTICAL CONSIDERATIONS	12
9. DATA MANAGEMENT.....	12
10. CHANGES TO THE CLINICAL INVESTIGATION PROTOCOL	13
11. DEVIATIONS FROM THE CLINICAL INVESTIGATION PROTOCOL.....	13
12. PROOF OF USE OF THE PRODUCT.....	13
13. DECLARATION OF CONFORMITY	13
14. PROCEDURE FOR OBTAINING CONSENT	14
15. ADVERSE EVENTS, ADVERSE EFFECTS OF THE PRODUCT AND PRODUCT DEFECTS..	14
16. POPULATION THAT CAN BE PRESSURED	14
17. PREMATURE TERMINATION OR SUSPENSION OF THE EXAMINATION	15
18. PUBLICATION POLICY	15
19. REFERENCES	15

1. Objectives and hypotheses of the clinical investigation

a) The aim of this prospective study is to evaluate the clinical performance of F-Composite 2, a proven flowable bulk material and adhesive system for the restoration of masticatory posterior fillings (Class I and II), all three materials being polymerized with Bluephase PowerCure (flash mode).

b) Primary hypotheses to be accepted or rejected by statistical data from the clinical investigation.

[name]. [name] from the Biostatistical Department of the Institute of Social and Preventive Medicine at the University of Lausanne, Switzerland, has performed a case number calculation. Assuming that a maximum of 10% post-operative hypersensitivity is acceptable, but actually only 5% is expected, the following formula can be used to calculate the case number (80% power, using a chi-square test at 5% probability of error)

$$N = (1.96 * \sqrt{0.95 * 0.05} + 0.84 * \sqrt{1 * 0})^2 / (1 - 0.95)^2 = 73 \text{ participants or fillings}$$

Furthermore, if one assumes - based on internal experience - that after one year there is a drop-out rate of 2%, 75 fillings are necessary at the beginning of the study to statistically confirm the primary endpoint (post-operative hypersensitivities).

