- Unexpected changes in the filling surface that could lead to roughness, discolouration or increased wear of the material. As the material is similarly polishable as a conventional composite material, it is expected that no more surface discolouration will be observed.

2. General overview of the clinical investigation

The F-Composite 2 system is a coordinated system of filling materials, adhesive and polymerization unit for direct restorative therapy in dentistry.

The aim of this single-arm prospective clinical study is to investigate the F-Composite 2 system in direct filling therapy of class I and II cavities.

The following working hypotheses should be clarified:

- Teeth restored with the F-Composite 2 system have postoperative hypersensitivity in a maximum of 10% of cases after 1 month, which corresponds to a frequency as described in the literature.
- With the selected application protocol, the F-Composite 2 system enables at least comparable restorative quality to F-Composite (see study "Clinical investigation of Flash Composite in direct restorative therapy" CEC-ZH No. 2011-0150/5.) After 2 years a maximum of 3 fillings should be replaced due to poor quality.
- The rate of loss of vitality after 1 year is maximum 1%, which corresponds to a frequency as described in the literature.

The clinical investigation will be conducted with a maximum of 75 patients. No more than two restorations will be placed in any one patient. For inclusion and exclusion criteria, see item "7.3 Participants".

Recalls take place after 6, 12, 24, 60 months.

Aftercare

At the end of the study period or when patients leave the study, they will continue to be routinely cared for by their private dentist.

3. Justification for the structure of the clinical investigation

In summary, it can be concluded from the literature cited in the investigator's brochure that restorative composites are suitable for the intended indications and show a clinically acceptable performance.

Up to now, polymerization of the adhesive or a composite increment takes 5 to 40 seconds, depending on the material used and the polymerization lamp used to cure the material. Currently, the upper limit of available light intensities for direct restorations is approximately 2'000 mW/cm². In a recent study from Norway (Kopperud et. al, 2017), in which 740 dentists from the public sector were interviewed, it was shown that these dentists exposed each composite increment for an average of 27 s.

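### Two fillings per patient are allowed, but the test in section 1 b) assumes independent fillings; if pairs occur and correlate positively, a filling-level test or interval is too precise

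*Combined protocol and SAP*

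**What the plan says.** Section 2 sets the limit: "No more than two restorations will be placed in any one patient". Section 7.3 a) repeats it among the inclusion criteria: "Maximum 2 restorations per patient". The sample is fixed in fillings. Section 8 b) says "The sample size is 75 fillings", and section 7.4 a) divides these among three operators at 25 each. Patients are only capped, at 75 (sections 2 and 7.3 g).

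Section 1 b) derives 73 "participants or fillings" from a binomial formula with no within-patient term, "using a chi-square test at 5% probability of error". After drop-out it concludes that "75 fillings are necessary at the beginning of the study to statistically confirm the primary endpoint". Section 8 a) then says "Due to the study design, no special statistical methods are necessary". Section 8 e) states the acceptance criteria as counts of fillings or teeth. No section says how two fillings in one mouth are to be handled.

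**The concern.** Participants and fillings are the same unit only if nobody receives two fillings. Since 75 fillings can come from anywhere between 38 patients (37 with two, one with one) and 75, the plan leaves open how much independent information it will hold. Two teeth in one patient share that patient's characteristics. Section 7.4 c) itself names age as a factor in hypersensitivity, and age is common to both teeth. It also names residual dentine thickness, which can differ between them, so the documents do not settle how strong the correlation would be.

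What is at stake is the stated precision of the primary rate: the error level of the chi-square test in 1 b), and the width of any interval reported at filling level. Clustering does not bias the observed rate itself.

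**Working it through.** **The plan's own figure.** As printed, the formula in 1 b) gives (1.96 × √(0.95 × 0.05) + 0)² / 0.05² = 72.99, so 73; and 73 / 0.98 = 74.5, so 75. Both reproduce. Whether those inputs suit a comparison of 10% with 5% is a separate question. No result below uses the 73.

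**Inputs.** From the documents: 75 fillings, at most two per patient, 10% acceptable rate, 5% expected rate, 5% error (1.96, so two-sided), acceptance at 6 or fewer. Assumed, because not given: k patients with two fillings, from 12 to 37, and ICC from 0.1 to 0.5.

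**Design effect.** With k pairs and 75 − 2k single fillings, DE = 1 + ICC × 2k/75.
- 12 pairs, ICC 0.1: 1 + 0.1 × 24/75 = 1.03; effective sample 75 / 1.032 = 72.7.
- 25 pairs, ICC 0.3: 1 + 0.3 × 50/75 = 1.20; effective sample 62.5.
- 37 pairs, ICC 0.5: 1 + 0.5 × 74/75 = 1.49; effective sample 50.2.

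**Rejection region.** Under a 10% rate the expected count is 7.5 and the binomial SD is √(75 × 0.1 × 0.9) = 2.598. The test rejects when the count is more than 1.96 × 2.598 = 5.09 from 7.5, that is at 2 or fewer, or at 13 or more. The Wilson interval inverts this test, so its non-coverage equals the test's error.

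**Exact enumeration.** Each pair has P(both affected) = p² + ICC × p(1 − p). Convolving k such pairs with 75 − 2k single fillings gives the distribution of the count.

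| Quantity | No pairs | 25 pairs, ICC 0.3 | 37 pairs, ICC 0.5 |
|---|---|---|---|
| P(2 or fewer), true 10% | 1.61% | 2.49% | 4.16% |
| P(13 or more), true 10% | 3.43% | 4.85% | 6.73% |
| Two-sided error (sum), true 10% | 5.0% | 7.3% | 10.9% |
| Wilson coverage, true 5% | 94.5% | 92.1% | 87.8% |
| Clopper-Pearson coverage, true 10% | 96.8% | 95.0% | 91.9% |
| Clopper-Pearson coverage, true 5% | 96.6% | 94.7% | 91.1% |
| P(6 or fewer), true 10% | 36.7% | 38.5% | 40.2% |
| P(6 or fewer), true 5% | 91.9% | 90.0% | 87.8% |

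The first row is the direction that matters for a claim that the rate lies below 10%; its nominal level is 2.5%.

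**At the acceptance limit.** For 6 of 75 (8.0%) the exact 95% interval is 3.0–16.6% unadjusted, 2.6–17.7% at DE 1.20 and 2.2–19.2% at DE 1.49.

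**The other two counts in 8 e),** at rates assumed for illustration, from no pairs to every possible pair at ICC 0.5: at most 1 vitality loss in 75 at a 1% rate, 82.7% to 78.4%; at most 3 replacements in 72 at a 2% rate, 94.4% to 90.5%.

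**The case against.** The strongest reply is that the harm needs three things the documents do not establish: pairs, positive correlation, and a reported filling-level test or interval. Section 8 names no test and no interval; its decision is a count, and counting needs no special method with or without pairs. On that reading 8 a) is correct for the rule that section 8 states. Much of this stands, and it is why the point is conditional. It does not dispose of the point, because 1 b) does name a test at a stated error level and says the sample serves to confirm the endpoint statistically. For that test, 8 a) is wrong if pairs occur.

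A second reply is that the choice of interval matters more than clustering in the middle of the range: plain Clopper-Pearson still covers 95.0% at a true 10% rate with 25 pairs and ICC 0.3. That stands. It falls materially short only near the upper end.

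Two stronger readings are tempting. A reader might infer that the acceptance decision is unsafe. The figures do not support that over the assumed range. Only perfect concordance in all 37 pairs moves the hypersensitivity rule at a true 10% rate by about 10 points (36.7% to 46.5%). A reader might also take section 8 g), which refers to "more than 50% of the patients suffer from postoperative hypersensitivity after placing at least 20 fillings", as proof that the units are confused. There the number of fillings can be read as a timing trigger and the share of patients as the measured quantity, so it proves nothing about the analysis.

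**Conclusion.** The point holds as a conditional one and is minor. If two-filling patients are enrolled and their outcomes correlate positively, a filling-level chi-square test or 95% interval is too precise: two-sided error of 7.3% to 10.9% instead of 5.0% at a true 10% rate, and 2.5% to 4.2% instead of 1.6% in the direction of concluding that the rate is below 10%, where only the upper figure exceeds the nominal 2.5%. These sizes rest on assumed values (25 pairs with ICC 0.3; 37 pairs with ICC 0.5). A reader might infer that the trial will in fact overstate its precision. The documents do not show that, since 75 patients with one filling each is within the cap and would remove the issue. The hypersensitivity acceptance rule shifts by at most about 4 points, so the market decision is little affected.

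**What to change.** Replace section 8 a) with text such as:

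> The filling is the unit of observation and the patient is the cluster. The number of patients with two fillings is reported. The primary rate is reported with a 95% Clopper-Pearson interval on the effective sample size (assessed fillings divided by the design effect). The design effect is the patient-clustered variance of the rate, with small-sample factor m/(m−1) for m patients, divided by its binomial variance, set to at least 1, and to 1 if there are no events. Any test of the 10% limit uses the same effective sample.

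Alternatively, state that each patient contributes one filling, which the cap of 75 permits; no adjustment is then needed.

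In 1 b), write 'fillings' in place of "participants or fillings" and say that the case number assumes independent fillings. Do not put an effective sample size beside the 73 unless the two are reconciled. At most, ask that the units in 8 g) be reconciled with those in 8 b) and 8 e); no position is taken on that rule.

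The cost is one calculation with the patient IDs already held (section 9 a) and no extra patients. The exact interval widens on average by under 1% with no pairs, about 11% with 25 pairs and ICC 0.3, and about 24% with 37 pairs and ICC 0.5. The repair is not perfect: coverage in that last case is 95.0% at a true 10% rate but 93.2% at 5%. Because it changes the statistical design, prior ethics approval may be needed under section 10.

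### Section 1 b) promises a 5%-level confirmation of the primary endpoint, but Section 8 decides on an observed count that a true 10% rate meets 37% of the time

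*Combined protocol and SAP*

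**What the plan says.** Section 1 b) gives the basis of the sample size: "Assuming that a maximum of 10% post-operative hypersensitivity is acceptable, but actually only 5% is expected", with "80% power, using a chi-square test at 5% probability of error". The printed formula returns 73. With 2% drop-out the section concludes that "75 fillings are necessary at the beginning of the study to statistically confirm the primary endpoint".

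Section 8 contains the analysis and the decision. Item a) states that the design calls for no special statistical methods. Item b) repeats the number: "The sample size is 75 fillings". Item c) gives the decision rule: "the system is suitable for the market if the acceptance criteria are met". Item e) lists three limits. The first, introduced as "Acceptance criterion for post-operative hypersensitivity after 4 weeks", is at most 10%, with 6 fillings in brackets. The other two are at most 1 tooth losing vitality by 1 year and at most 3 fillings replaced by 2 years. Nothing in the document ties the decision to a p-value or a confidence limit.

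**The concern.** The sample size is defended by the properties of a test, but the decision does not use that test. An observed rate at or below 10% is not evidence, at 5% error, that the true rate is at or below 10%. With 75 fillings the two can be far apart.

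The study has no control group, so the fixed limit is the only formal safeguard on the primary endpoint. Section 6 c) says that the hypersensitivity risk cannot be settled in vitro and that this is why the study is needed. If the count is met and the result is reported as statistical confirmation, readers will credit it with a 5% error that the rule does not have.

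**Working it through.** **Inputs.** Maximum acceptable rate 10%, expected rate 5%, error 5%, power 80%, drop-out 2% (Section 1 b). 75 fillings, and a limit of at most 10% printed as 6 (Section 8 b and e). Since 0.10 × 75 = 7.5, the percentage alone would allow 7.

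**The plan's own figure.** (1.96 × √(0.95 × 0.05) + 0.84 × √(1 × 0))² / (1 − 0.95)² = 72.99, so 73. Then 73 / 0.98 = 74.5, so 75. Both numbers reproduce. However, the rates entered are 0.95 and 1, which is 5% versus 0% events, and the power term is 0.84 × 0 = 0. With the rates named in the text, the same formula gives (1.96 × √(0.10 × 0.90) + 0.84 × √(0.05 × 0.95))² / 0.05² ≈ 238 (239 with unrounded normal quantiles). With 1.645 in place of 1.96 it gives 184.

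**What the count rule does.** Let X be the number of events among 75 independent fillings, X ~ Binomial(75, p). The criterion is met if X ≤ k, with probability Σ C(75, x) pˣ (1 − p)⁷⁵⁻ˣ for x = 0 to k.

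| True rate p | P(X ≤ 6) | P(X ≤ 7) |
|---|---|---|
| 5% | 91.9% | 96.6% |
| 10% | 36.7% | 52.1% |
| 11% | 26.9% | 40.9% |
| 12% | 19.0% | 30.9% |
| 15% | 5.4% | 10.8% |

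Under the printed count, the chance of meeting the criterion falls to about 5% only near a true rate of 15%. With 73 evaluable fillings the figures at 10% are 39.6% and 55.2%.

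**What a passing result excludes.** Exact (Clopper-Pearson) one-sided 95% upper limits are 15.2% for 6/75 and 16.8% for 7/75.

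**What would deliver the stated error at 75 fillings.** P(X ≤ 2) at p = 10% is 1.6%; P(X ≤ 3) is 5.04%, just over 5%. The interval agrees: 3/75 has an upper limit of 10.01%, 2/75 has 8.2%. The cut-off is therefore at most 2 events, and its power at a true 5% is 27.0%. The 1.96 in the formula implies a two-sided 5% test, that is 2.5% in the favourable direction; the cut-off is still 2.

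**What 80% power would need.** The first sufficient exact design is 179 fillings with at most 11 events (one-sided 5%: error 4.9%, power 81%), or 231 with at most 14 (one-sided 2.5%: error 2.4%, power 82%). Section 2 caps the study at 75 patients with at most two restorations each, so 75 × 2 = 150 fillings. Neither design fits.

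**Clustering.** As an illustration, assume 37 patients with two fillings and one with one, and a within-patient correlation of 0.1 to 0.5. By simulation, the pass probability at 10% is about 38–40% (≤6) and 52–53% (≤7).

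**The case against.** A fixed acceptance count is a legitimate rule for a single-arm device study, and this one passes a product at the expected 5% rate 92% of the time. That stands: the rule can be kept. What cannot stand beside it is the claim of a 5%-level test and statistical confirmation.

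A reader might infer that an unacceptable product reaches the market 37% to 52% of the time. The documents do not support this, for three reasons. First, Section 1 b) calls 10% the maximum acceptable rate, so a product at exactly 10% is within the plan's limit. Error is conventionally evaluated at that boundary, but rates above it pass less often, as the table shows. Second, the printed count is 6; the 52% applies only if the percentage overrides it. Third, Section 8 c) also requires the vitality and replacement limits to be met, so the pass probability of one criterion is an upper bound for the whole decision.

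A reader might also infer that the replacement and vitality limits break the same promise. They do not. Section 1 b) attaches its error and power to the primary endpoint only, and the plan states no error rate for the other two.

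Finally, it would be wrong to conclude that a sound calculation for 10% versus 5% exists and only the test was left out. The printed formula is not that calculation.

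**Conclusion.** The concern holds as an inconsistency between Section 1 b) and Section 8. The primary criterion is met 37% of the time at the boundary rate of 10% on the printed count (52% with 7), against a stated 5%. At a true 12% it is still met 19% (31%) of the time. The stated 5% error and 80% power cannot both be had with 75 fillings: holding the error leaves 27% power. The figures rest on 75 evaluable and independent fillings. Slightly fewer fillings, or moderate correlation within patients, raises the pass probability a little and does not change the conclusion. They describe the hypersensitivity criterion only and bound the overall market decision from above.

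**What to change.** Keep 75 fillings and make the claim match the rule.

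1. In 8 e), settle on one count and state its properties. For at most 6: 37% pass at a true 10% and 92% at 5%. For at most 7: 52% and 97%.
2. In 1 b), remove or restate the 5% error, the 80% power, the chi-square test and the confirmation wording as one change; removing only some of them would leave a power claim without a test. Correct the formula in the same edit. Because 10% versus 5% does not yield 73, justify 75 by the properties in item 1 and the width of the exact interval.
3. In 8, report the primary rate with an exact confidence interval, and the two secondary rates likewise as description.
4. State that a rate below 10% is statistically shown only if the exact one-sided 95% upper limit is below 10%. At 75 fillings this means at most 2 events (error 1.6%, power 27% at a true 5%); 3 events give 10.01% and fail.

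The cost is wording in two sections and three intervals, with no extra patients. The downside is that the stated error and power become less favourable, and a result of 3 to 6 events would meet the acceptance limit without showing statistically that the rate is below 10%.
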